# **Detailed Project Description**

# Changes since outline submission:

This full proposal is a merger of two outline proposals previously submitted from the North West Region (05/41/02 and 05/41/03) and is led jointly by [name] and [name]. For purposes of communication, [name] has been nominated as the Principal Investigator. The revised study design is a synthesis of both previous protocols and incorporates comments from Commissioning Board Members. The Study Centre will be based at the North West Quality Assurance Reference Centre, The Liverpool Women's Hospital Foundation Trust, Liverpool. The study will be managed by a full-time Research Manager (grade 6 pt 3) assisted by a full-time Clerical Assistant (grade C). The Study Management Group will comprise all members of the study team, together with the Research Manager and Clerical Assistant. The budget will be held by [name], Professor of Gynaecological Oncology, University of Manchester. Data handling and statistical evaluation will be undertaken by [name], Biostatistics Group, University of Manchester and [name], Wolfson Institute of Preventative Medicine. A Research Assistant will be employed for a 6month period to assist with the data handling and statistical evaluation. An epidemiological, public health and screening overview is provided by [name] for the Public Health Department, Government Office North West. The costing includes £5,000 for the production and maintenance of a number of databases which will be used both to document the many different slide sets and for direct data entry at the study sites. There is a further 6 months of BMS 3 and BMS 1 time for the production of and assistance in the detailed cataloguing of slide sets in part 2 of the study.

# **Relevance to Commissioning Brief:**

This proposal addresses all aspects of the commissioning brief as follows:

- Current working practice in a large number of laboratories throughout England, Scotland and Wales will be surveyed to determine what minimum cellularity levels are currently being used to assess whether an LBC sample is adequate.
- The reasons for the choice of minimum cellularity by these laboratories will be examined.
- A comparison of declared and actual practice will provide evidence of how closely laboratories adhere to these local guidelines.
- In the second part of the study, multiple slides will be prepared from individual samples to assess the impact of overall cellularity; relative proportion of abnormal cells; and the type and presentation of abnormal cells on the ability of primary screeners to routinely detect those abnormalities.
- This will provide an estimate of the level of cellularity at which a satisfactory pick-up rate of high and low grade disease can be detected
- It will also allow the estimation of a level of cellularity which minimises samples being wrongly labelled 'negative' when they are inadequate.
- The study will compare both of the current LBC platforms and will assess any operational differences relating to cell counting.
- The study will establish a reliable method of determining the total cellularity for both current LBC systems.
- The use of transformation zone indicators as a quality indicator of smear taker practice will also be examined.

# **Objectives:**

- To assess current standards and practice for the reporting of LBC preparations across England, Scotland and Wales
- To determine the cellularity of samples deemed inadequate, negative or abnormal by a range of laboratories across the country.
- To determine the cellularity of samples deemed negative, HPV+ in the ARTISTIC/MCM trial.
- To assess the impact of varying the overall cellularity; relative proportion of abnormal cells and the type and presentation of dyskaryotic cells on their likelihood of detection.
- To determine the threshold of cellularity of LBC preparations which allow the majority of samples containing abnormal cells to be detected by routine screening.
- To establish a reproducible method for rapidly estimating the cellularity of an LBC sample.

# **Background and Introduction:**

Criteria for the assessment of adequacy of a cervical sample have been widely discussed over the years and remain the subject of debate. While there is general agreement, that for routine screening the squamous cell content is the primary indicator of adequacy, there is no clear agreement as to the definition of an adequate cervical sample in respect of Liquid Based Cytology (LBC). At a pragmatic level, it may best be defined as the minimum acceptable squamous cellularity which will allow the detection rate for squamous abnormalities to be at least as good as that for conventional cervical smears.

The current version of the Bethesda Terminology system  requires a minimum of 5,000 squamous cells for a liquid based preparation to be deemed 'satisfactory'. However, this figure appears to be based on anecdotal experience  rather objective evidence. Cervical Screening Wales and some regions in England, including the North West, have adopted an interim figure of 15,000 cells pending definitive guidance. The Scottish Cervical Screening Programme, which only uses Cytyc ThinPrep® as its sole LBC technology, uses a figure of 5,000 cells. Even within these declared values there is considerable variation and subjectivity as to the assessment of cellularity. This uncertainty inevitably leads to variable repeat smear rates and has capacity and funding implications for the local providers of these screening programmes.

The NICE Technology Appraisal (2003) concerning the use of LBC for cervical screening recommended its use as the primary means of processing samples in the screening programmes in England and Wales and gave a completion date of October 2008. Wales has already achieved full implementation. Many regions in England are either in the process of conversion or are near to full conversion. Scotland converted in 2004. There is thus an ever growing requirement for definitive guidance on cervical sample adequacy.

# **Setting:**

The study will encompass a large number of NHS Acute Trust laboratories which participate either in the NHS Cervical Screening Programme, the Scottish Cervical Screening Programme or Cervical Screening Wales and which have implemented Liquid Based Cytology (LBC) for population based cervical screening.

# **Target Population:**

LBC samples and slides will be obtained from women between the ages of 25-64 who have presented for routine cervical screening. All such women will have received a copy of 'The Facts' leaflet or national equivalent which gives implied consent for cervical screening.

#### **Ethical considerations:**

This study uses both archived slides and 'residual' tissue from cases which have already been reported and patient management previously defined. Neither part of the study will review nor aim to challenge existing diagnoses and hence neither will have clinical or management implications for individual women. However, one of the aims of the study is to improve the reliability of those samples assessed as negative. This is likely to be of long-term benefit to all women participating in the national cervical screening programmes.

An application will be submitted to the Liverpool Research and Ethics Committee in respect of the second part of the study as this uses 'residual' tissue which would normally be discarded once the final report was issued. Individual patient consent will not be required. The Human Tissue Act 2004 states that 'consent is not needed for the use of 'residual' tissue in **research**, provided that the research project has ethical approval, and that the researcher cannot identify the tissue donor and is not likely to be able to do so in the future'. All material (slides and residual tissue) will be anonymised on accessioning to the study. There will be no use of named patient data in any part of the study.

# **Health Technologies being assessed:**

The study will assess material and slides from the only two LBC systems currently in use in the UK; the Cytyc ThinPrep® LBC system and the SurePath™ LBC system.

# HTA brief, part 1: to survey which thresholds are used in current practice at laboratories using LBC and the reasons for their choice of threshold

The first part of the study surveys current working practice to establish both the declared formal laboratory thresholds for LBC specimen adequacy and the active thresholds which are operating in practice, with a view to determining the respective levels of each and whether they are different.

It also establishes cohorts of inadequate, negative and abnormal cases which have been reported in a routine screening setting for which total cell counts are known. This information will supplement that from part 2 and will provide an estimate of screening sensitivity at different levels of cellularity.

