# Design:

# **Laboratory Practice Survey**

This part of the study will be conducted in England through the national network of Regional Cervical Screening Quality Assurance Directors, and in Wales and Scotland through Cervical Screening Wales and the Scottish Cervical Screening Programme respectively. A total of 39 laboratories from the 9 English QA regions, 7 from Scotland and 10 from Wales to be recruited to ensure an approximately even representation of the two current LBC systems, giving a total of 56 laboratories (28 laboratories for each system). They will include a cross-section of low, intermediate and high workload laboratories and all will have implemented LBC for population based cervical screening for a minimum of 6 months post LBC training and accreditation. This will avoid recognised learning curve issues. The suggestion that the NHS LBC pilot sites and training centres should supply the bulk of the cases is impractical given the substantial imbalance in representation of the two LBC companies across those sites and would be likely to greatly extend study timescales.

All participating laboratories will be asked to nominate a Study Liaison Officer and a deputy. These persons will normally be senior BMS staff and will act as the contact point for all communication with the LBC Adequacy Study Centre. Each laboratory will initially be asked to complete a questionnaire which will cover the following points:

- Type of LBC system used
- Approximate date of completion of LBC training
- Date of full conversion to LBC
- Criteria used in laboratory for assessing adequacy including declared threshold, with copy of relevant laboratory Standard Operating Procedure (SOP)
- Copy of any other relevant SOPs e.g. cell counting methodology
- Current KC61 figures (DH return giving laboratory performance data) or equivalent data but to include only LBC cases (some labs may not have full 12 months LBC data)

Additional laboratories may be recruited to increase the total number undertaking slide assessments and to spread this workload more widely. The same requirements for study entry will apply as stated above, but these laboratories will not be asked to complete a questionnaire or to submit slides. It will be important to ensure an approximately even representation of the two LBC

[figure not shown]

Figure 1- Examples of normal and additional slide labels

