# **Slide Survey**

The 56 participating laboratories will be asked to submit 20 consecutive cervical screening LBC cases from each of the following report categories: inadequate, mildly dyskaryotic and high grade (moderate dyskaryosis and above). All high grade cases must be histologically confirmed. While histological confirmation of the mildly dyskaryotic cases is preferable it is acknowledged that this may not always be possible. It is important that as many cases as possible and certainly all high grade abnormalities are histologically proven to validate outcome. If outcome were determined by expert panel this could easily lead to a change in the original proffered diagnosis. This has serious and potentially negative implications for submitting laboratories and could lead to some declining participation.

Slides reported as borderline nuclear change will not be included in the study as this is a much less robust diagnostic category than higher grade abnormalities and its use is not consistently applied across laboratories.

50 consecutive negative cervical cytology LBC cases from the same time period will also be requested from each of these laboratories. They will be asked specifically not to pre-select good examples of individual diagnostic categories but to adhere strictly to number sequences. A total of 110 slides will thus be provided by each of the 56 laboratories resulting in a total of 6,160 slides in this arm of the study. Laboratories will have 3 months to gather and submit these slides.

Cases reported as inadequate because of the absence of transformation indicators following previous treatment of CIN, or the absence of endocervical cells in the case of previously treated CGIN will be specifically excluded from the study as the reason for inadequacy does not relate to specimen cellularity.

It is recognised that mucus and blood may block the filter pores in the Cytyc ThinPrep® LBC system. This problem should be addressed in routine work by the pre-treatment of the sample prior to a repeat preparation being made. The study will collect both the original preparation and any repeat preparations which have been made.

If additional preparations have been made, then all available slides should be submitted and included within the category of the issued cytological report, irrespective of the appearance of individual slides.

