# Sample Size

Declared inadequate slides will be used to determine the distribution of cellularity in such slides. With a sample of 1,120 a proportion of say 5% falling above the specified threshold can be estimated with a 95% distance from the percentage to the 95% c.i. of 1.3%. Declared negative slides will be used to estimate the proportion falling below the specified threshold. With 2,800 slides a proportion of 1% falling below the required threshold can be estimated with distance from the percentage to the 95% c.i. of 0.4%. We hypothesise that the greatest proportion of slides with low cellularity will be seen in mildly dyskaryotic slides and lowest proportion in negative slides, with high-grade dyskaryotic slides between the two. With 2,800 negative slides, 1,120 high grade and 1,100 mildly dyskaryotic slides, a chi-squared test of trend will have a power of 87% to detect a difference between 1% of negative slides falling below a threshold increasing to 2.5% in the mildly dyskaryotic cases and a power of 74% to detect an trend increasing from 1% to 2%.

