# **Summary of Project:**

The first part of the study surveys current working practice to establish both the declared laboratory thresholds for LBC specimen adequacy and those thresholds which are operating in practice, with a view to determining the respective levels of each and whether they are different.

It also establishes cohorts of inadequate, negative and abnormal cases which have been reported in a routine screening setting for which total cell counts are known. This information will supplement that from part 2 and will provide an estimate of screening sensitivity at different levels of cellularity.

The second part of the study will assess the contribution of differing total cellularity; relative proportion of abnormal: normal cells; and dyskaryotic sub-type on the likelihood that the slide will be categorised as abnormal. Slide sets comprising serial dilutions of known abnormal cases and of preparations with varying ratios of dyskaryotic to total squamous cells will be assessed by independent review panels. The results will allow an estimate of a level of cellularity at which most abnormalities are likely to be detected and will provide an evidence base to inform national guidance relating to the minimum acceptable cellularity for a cervical LBC sample.

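### Part 1 samples slides by issued report, so it cannot estimate sensitivity by cellularity, and its trend test can reject because low-cell slides leave the negative group as inadequates

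*Protocol*

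**What the plan says.** The introduction to Part 1 (HTA brief, part 1) says of the inadequate, negative and abnormal cohorts: "This information will supplement that from part 2 and will provide an estimate of screening sensitivity at different levels of cellularity". The Summary of Project repeats that this information "will provide an estimate of screening sensitivity at different levels of cellularity".

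Under Slide Survey, each of 56 laboratories is to "submit 20 consecutive cervical screening LBC cases from each of the following report categories" (inadequate, mild, high grade), and "50 consecutive negative cervical cytology LBC cases from the same time period will also be requested from each of these laboratories". Where several preparations exist, all are "included within the category of the issued cytological report, irrespective of the appearance of individual slides". On verification, "All high grade cases must be histologically confirmed"; histology is preferred for mild cases; nothing is required for negatives or inadequates. Ethical considerations adds that existing diagnoses will not be reviewed.

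The Part 1 Sample Size section hypothesises that the "greatest proportion of slides with low cellularity will be seen in mildly dyskaryotic slides and lowest proportion in negative slides", with high grade in between, and gives the power of a chi-squared trend test across those three groups. Inadequates are not in the test. The Part 1 Statistical Analysis section models the proportion of slides either side of a threshold, with smear result as a covariate, at each laboratory's current threshold and at the one derived in Part 2. It contains no sensitivity estimate.

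**The concern.** Sensitivity at a given cellularity is the probability of an abnormal report given disease and that cellularity. Every dyskaryotic slide in the laboratory cohorts was, by selection, detected. Disease among slides reported negative or inadequate is not identified, and the category sizes are set by quota. The missing part of the denominator cannot be recovered by analysis.

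The trend test has a related difficulty. A sparse slide with no visible abnormality tends to be reported inadequate and so leaves the negative group. A sparse slide with visible dyskaryosis can still be reported abnormal. Comparing the percentage below threshold in negatives with that in abnormals therefore compares a group filtered on cellularity with groups filtered less, or not at all.

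The study is meant to inform national guidance on minimum cellularity. A sensitivity figure from Part 1, or a significant trend taken as evidence on detection, would give that guidance support which the sampling cannot supply.

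**Working it through.** **Inputs.** From Part 1 Sample Size: 2,800 negative, 1,120 high-grade and 1,100 mild slides (56 × 20 = 1,120, so 1,100 looks like a slip; it is kept here); 1% of negatives below threshold; 5% of inadequates above it, hence 95% below. From Summary in Plain English: an LBC inadequate rate of 1-2%. Assumed, because not stated: two-sided 0.05, scores 0, 1, 2 for negative, high grade, mild.

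**The plan's own figures first.** Interval half-width = 1.96 × √(p(1−p)/n).
- Inadequates: 1.96 × √(0.05 × 0.95/1,120) = 1.28% (stated 1.3%).
- Negatives: 1.96 × √(0.01 × 0.99/2,800) = 0.37% (stated 0.4%).

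Trend power, Cochran-Armitage normal approximation with high grade at the midpoint: 92% for 1% to 2.5% (stated 87%) and 69% for 1% to 2% (stated 74%). The high-grade proportion is not given. Each stated power can be matched under some choice, but no single natural convention was found that gives both. Nothing below depends on these powers.

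**Returning inadequates to the non-abnormal pool.** With inadequate rate r, the proportion below threshold is (1 − r) × 1% + r × 95%:
- r = 1%: 0.99% + 0.95% = 1.94%
- r = 1.5%: 0.985% + 1.425% = 2.41%
- r = 2%: 0.98% + 1.90% = 2.88%

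These are of the same size as the rises from 1% to 2% and 2.5% for which the test is powered.

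**Rejection with no real relation.** Give high-grade and mild slides the pooled proportion q, and keep declared negatives at 1%. The statistic is U = Σ nᵢpᵢ(sᵢ − s̄), with s̄ = 3,320/5,020 = 0.661, null variance p̄(1 − p̄) × Σ nᵢ(sᵢ − s̄)², and Σ nᵢ(sᵢ − s̄)² = 3,324. For q = 1.94%: U = 17.41, null SD 6.81, SD under the alternative 7.22. The rejection probability is Φ((17.41 − 1.96 × 6.81)/7.22) = Φ(0.56) = 71%. Simulation with 200,000 runs gives:

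| Inadequate rate | All low-cell abnormal slides still reported abnormal | Half of the excess over 1% retained |
|---|---|---|
| 1% | 71% | 28% |
| 1.5% | 94% | about 50% |
| 2% | 99% | 71% |

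With 1% in all three groups the same simulation rejects in 5% of runs.

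**A lower cellularity-related rate.** Slide Survey excludes inadequates due to absent transformation-zone indicators or endocervical cells after treatment, so the rate relevant to cellularity may be below 1-2%. The excluded share is not given. As an illustration with full retention, r = 0.5% gives 1.47% below threshold and 28% rejection; r = 0.75% gives 1.705% and 51%.

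**The case against.** The strongest reply on sensitivity is the ARTISTIC/MCM section. Part 1 includes 1,200 smear-negative, HPV-positive cases, which the protocol regards as genuine false negatives, to be counted and compared with the Part 1 negative and mild slides. A reader might infer that Part 1 contains no missed abnormalities at all; that goes too far. What stands is a relative comparison of false-negative with detected slides. It is limited: the cases come from another trial, that trial used ThinPrep only (Part 2 Design), and HPV positivity is not confirmed disease. It does not give sensitivity by cellularity, and offers nothing for SurePath.

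A second reply is that the harm is not in the analysis plan. Part 1 Outcome Measures concern adherence to declared and derived thresholds, the cellularity estimate belongs to Part 2, and the disputed sentence speaks of supplementing Part 2. No section says that a significant trend will be read as evidence on detection. This is fair, and it makes the remedy mainly one of wording. The sensitivity claim is still made without qualification in two places.

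On the trend test, a reader might infer that it is bound to be positive. The documents do not support that. They do not say that low-cell abnormal slides are always reported abnormal; the 5% is offered as an example value; the exclusions lower the relevant inadequate rate; and at a Part 2 threshold differing from a laboratory's working threshold, negatives are not cut at the tested value. The mechanism as modelled also puts mild and high grade level, so it does not reproduce the hypothesised order between them.

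**Conclusion.** The sensitivity statement is wrong as written: the Part 1 laboratory cohorts give cellularity given the report, and the ARTISTIC/MCM set adds only a relative comparison. This conclusion needs no numerical assumption.

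The trend test is open to a selection effect as large as the effect it is designed to find. The size is conditional. Rejection without any real relation ranges from 71-99% under full retention of low-cell abnormal slides to 28-71% under half retention, for inadequate rates of 1-2% and the plan's illustrative 1% and 95%. It is lower if the cellularity-related inadequate rate is under 1%, or may be where the Part 2 threshold differs from working thresholds. A significant trend is therefore not interpretable as a link between cellularity and abnormality, though it is not guaranteed to occur. The descriptive cell counts by report category and the comparison of declared with actual thresholds remain valid.

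**What to change.** 1. Delete the sensitivity claim for Part 1 in the HTA brief, part 1 introduction and in the Summary of Project. State that sensitivity by cellularity comes from Part 2, where abnormality is known before reading. Keep the ARTISTIC/MCM comparison as supplementary and relative, with its ThinPrep-only and unconfirmed-disease limits stated.
2. Describe the negative/high-grade/mild trend as a comparison of report categories and of adherence to threshold, not as evidence on detection.
3. Add a sensitivity analysis with negatives plus inadequates as comparator, weighted to each laboratory's report rates. The questionnaire already requests these: "Current KC61 figures (DH return giving laboratory performance data" or equivalent, LBC cases only. The protocol does not show that these returns separate inadequates by reason, so an unadjusted overall rate could over-weight low-cell slides. Run the analysis over a stated range for the share of inadequates excluded under Slide Survey.

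The cost is wording and one extra analysis, with no new slides. The downside is wider intervals and dependence on the assumed excluded share.
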